### 8.2.1 Inclusion criteria

- Ability to understand the nature of the study.
- Willingness to provide written informed consent.
- Patients undergoing HUTT for monitoring of syncope, therapy adjustment, training or other medical reasons during ordinary follow-up, irrespective of study participation
- Patients who participated in the BIOSync study\*.
- Patients with a dual-chamber pacing system equipped with the CLS algorithm.

\* If needed, inclusion of other patients who did not participate in the BIOSync study will be considered to complete study cohort, provided that they have already a CLS pacemaker system and fulfill the same inclusion/exclusion criteria of the BIOSync study.

### 8.2.2 Exclusion criteria

- Pregnant or breast feeding women.
- Age less than 40 years.
- Patients who after the BIOSync study participation have developed the following:
  - Any indication to pacemaker different from reflex syncope with positive HUTT response; or
  - Any classified indication to implantable defibrillator, cardiac resynchronization therapy according to current guidelines; or
  - Any cardiac dysfunctions likely leading to loss of consciousness (overt heart failure, ejection fraction <40%, myocardial infarction, diagnosis of hypertrophic or dilated cardiomyopathy, clinically significant valvular disease, sinus bradycardia <50 bpm or sinoatrial block, Mobitz I second degree atrioventricular block, Mobitz II second or third-degree atrioventricular block, complete bundle-branch block).

### 8.2.3 Criteria and procedures for subject withdrawal

#### 8.2.3.1 Withdrawal of patient consent

Patients may withdraw their consent for study participation at any time without stating the reason and without any unfavourable consequences. All data that is collected until the date of withdrawal will be deleted immediately by effective anonymization, unless their further processing is still required as regulated by the legal exceptions to the deletion obligations. This also applies if the patient has requested data erasure. Depending on the patient's decision to delete the data, it will be deleted by effective anonymization as soon as the conditions for the

legal exceptions on further retention and processing cease to apply. A withdrawal sheet and a study termination CRF have to be filled in by the investigational site.

#### 8.2.3.2 Impossibility of device programming at enrolment visit

If during the enrolment visit a device programming according to Table 2 (as reported in section 9.2.2) is not possible for any reason, the patient shall terminate study participation before performing the HUTT (dropout).

#### 8.2.4 Point of enrollment

[figure not shown]
A subject is considered enrolled in the BIO|Sync-HUTT Study upon the signature of the Informed Consent Form after confirmation of the eligibility criteria by the investigator.

#### 8.2.5 Total expected duration of the clinical investigation

The expected total duration of the study is 19 months after the first enrolment.

#### 8.2.6 Expected duration of each subject's participation

Subjects participate from consent to HUTT execution with not further follow-up. Figure 1 shows the flowchart of the study.

**Figure 1:** Flowchart for the BIO|Sync-HUTT study

#### 8.2.7 Number of subjects required to be included

A maximum of 20 subjects will be enrolled (including replacements as described in section 8.1.6). Please refer to section 12.5 for further details on the planning of the sample size.

#### 8.2.8 Estimated time needed to select patients

The enrolment period is expected to last 9 months.

## 9 STUDY PROCEDURES

### 9.1 Overview

This section describes all the study-related procedures as listed in Table 1 which will be performed during a routine scheduled patient follow-up.

Prior to obtaining informed consent, the patient's background and medical history will be reviewed in order to ensure he/she is an appropriate candidate for the study. Patient who undergo HUTT during ordinary follow-up visits irrespective of study participation, is eligible. After the patient has been determined to be eligible for the study, written informed consent will be obtained and demographic and medication data will be collected. Syncope and pre-syncope questionnaires will be self-administered. Prior to the HUTT, pacemaker interrogation will be performed in order to check programming settings and to collect device diagnostics. The HUTT may be performed and also recorded by a high-definition camera if available. Full hemodynamic parameters and ECG traces will be acquired during the HUTT. Any collected data and adverse events will be documented in an electronic CRF.

**Table 1: Investigation Schedule**

Investigations	Enrollment/study visit
Verification of in- and exclusion criteria	X
Patient informed consent	X
Demographic data	X
Medical history	X
Co-morbidities	X
Medication therapy	X
Patient self-administered syncope and pre-syncope questionnaires	X
ECG	X
Device programming settings and diagnostics	X
Head-up tilt test (including video recording if available)	X
Collection of primary and secondary endpoint-related measurements	X
(S)AE, (S)ADE, DD monitoring	X

## 9.2 Enrollment/study visit

### 9.2.1 Baseline assessment

The baseline data will be collected after consenting procedures are completed.

For baseline evaluation, the investigator collects the following data on an CRF:

- Demographic data
- Medical history
- Comorbidities
- Cardiomyopathies
- Arrhythmias
- Prior ECG
- Medication therapy
- Syncope and pre-syncope questionnaires
- Previous participation in the BIOSync study
- Date of pacemaker implantation
- Device programming

### 9.2.2 Study procedures after baseline assessment

The following procedures shall be conducted after baseline assessment:

- Interrogate the pacemaker and save the pacemaker diagnostics;
- Make sure that the DDD-CLS pacing mode has been activated since for at least 10 days. If the CLS mode is not active or any pacing mode other than DDD-CLS is active at the time of interrogation, reprogram the device as reported in the Table 2 below, and reschedule a new visit in at least 10 days to perform the HUTT. If device programming according to Table 2 is not possible for any reason, the patient shall terminate study participation before performing the HUTT (dropout).
- Perform standard tests to assess correct pacing and sensing function with current settings;
- Check that the device programming is set as reported in Table 2. Parameters which are not listed have to be intended freely selectable\*;
- Switch off the programmer;
- Perform the head-up tilt testing as reported in section 9.2.3;

**\* Note: any device re-programming involving a switch from CLS-OFF to CLS-ON or a change in the CLS-mode pacing will require to postpone HUTT execution for at least 10 days. Any other device re-programming according to table 2 will require patient to wait 10 minutes in a sitting position before HUTT execution due to the time period needed to fine-tune impedance reference waveforms. Also it shall be ensured that the nominal AV-delay (excluding hysteresis) is programmed sufficiently short (intrinsic conduction time minus at least 43 ms) in order to avoid fusion beats.**

As per standard of care, PM programming will be optimized if needed, according to observations collected during the HUTT.

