#### 8.1.2 Measures taken to minimize or avoid bias

Accurate patient selection as described in section 8.2 and precise conduction of HUTT according to the procedures described in section 9 will allow to minimize potential confounding factors.

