**Table 2 – Device programming**

Parameter	
Pacing Mode	DDD-CLS
Basic rate	50 bpm
Maximum CLS rate	120 bpm
Upper tracking rate	130 bpm
Atrioventricular delay	Low; 180–140 ms
Atrioventricular hysteresis mode	IRSplus
CLS Resting Rate Control	OFF
Atrial pacing polarity	Unipolar
Ventricular pacing polarity	Unipolar

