## 15 DEVIATIONS FROM CLINICAL INVESTIGATION PLAN

### 15.1 CIP compliance and exceptions

All sponsor personnel, all investigational site personnel as well as other third parties, who are involved in tasks covered by this CIP, are generally obliged to comply with this CIP.

A deviation is any failure to follow, intentionally or unintentionally, the requirements of the CIP, including laws, guidelines and other regulation as far as required by the CIP and applicable laws, as well as applicable amendments. Deviations that are likely to seriously affect or that actually have seriously affected the rights or safety or wellbeing of patients or the scientific integrity of the clinical investigation are major deviations. Otherwise they are minor deviations.

Erroneous, spurious or missing data in a CRF is not a deviation in itself and is handled according to the query processes described in the data management section of this CIP. However, the underlying reason might be a deviation.

Under emergency circumstances, deviations from the CIP to protect the rights, safety and well-being of human patients may proceed without prior approval of the sponsor and the ethics committee.

No waivers from the CIP are allowed.

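### Do the AV delay in Table 2 and the fusion-beat note in Protocol 9.2.2 contradict each other?

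*Protocol*

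**What the plan says.** The procedure in Protocol 9.2.2 is: "Check that the device programming is set as reported in Table 2. Parameters which are not listed have to be intended freely selectable". An asterisk on that item leads to a note. Table 2 lists the AV delay as low, 180 to 140 ms, and has a separate row "Atrioventricular hysteresis mode".

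The note makes three points. A change affecting CLS activation or mode postpones the tilt test by at least 10 days. "Any other device re-programming according to table 2" calls for a 10-minute seated wait. Finally, sites must ensure that the "nominal AV-delay (excluding hysteresis) is programmed sufficiently short (intrinsic conduction time minus at least 43 ms".

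Protocol 8.2.3.2 adds that if programming to Table 2 "is not possible for any reason, the patient shall terminate study participation before performing the HUTT (dropout"; 9.2.2 repeats this. The conduction criteria in Protocol 8.2.2 include "Mobitz I second degree atrioventricular block, Mobitz II second or third-degree atrioventricular block, complete bundle-branch block". None of the listed criteria sets a lower limit on conduction time.

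**The concern.** Both instructions are mandatory, and AV delay is a listed parameter, so it is not among those left free. In a patient with fairly short intrinsic conduction, the note calls for a delay below anything Table 2 shows. The hysteresis row does not help, because the note counts the delay without hysteresis.

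Two sites could then treat the same patient differently: one keeps the table, the other keeps the note, and a third might invoke the dropout rule. Protocol 8.1.2 rests its control of bias on the claim that "precise conduction of HUTT according to the procedures described in section 9 will allow to minimize potential confounding factors". Protocol 15.1 says "A deviation is any failure to follow, intentionally or unintentionally, the requirements of the CIP" and allows no waivers. On the hard-limit reading, whichever instruction gives way is a deviation, so the deviation record would depend on how a site reads an asterisk. With enrolment capped at 20 (Protocol 8.2.7) and 15 fully analysable data sets wanted (8.1.6), dropping patients on a misreading could also cost data.

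**Working it through.** The plan states no conduction-time threshold, so there is no figure to reproduce.

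**Inputs.** Shortest and longest AV delay in Table 2: 140 and 180 ms. Margin in the note: 43 ms. T is a patient's intrinsic conduction time; the documents give no values for it. Assumption: T and the programmed delay are measured on the same basis, which the documents do not define.

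**Formulas.** The note caps the delay at T − 43.

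- Entry read as a permitted range: both instructions can hold if T − 43 ≥ 140, so T ≥ 183 ms. Shortfall = max(0, 183 − T).
- Entry read as one setting with a nominal value of 180 ms: both hold if T − 43 ≥ 180, so T ≥ 223 ms. Shortfall = max(0, 223 − T).
- Entry qualified by the note: no conflict at any T.

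| T (ms, assumed) | Cap T − 43 | Shortfall, range | Shortfall, nominal 180 |
|---|---|---|---|
| 160 | 117 | 23 | 63 |
| 170 | 127 | 13 | 53 |
| 182 | 139 | 1 | 41 |
| 183 | 140 | 0 | 40 |
| 190 | 147 | 0 | 33 |
| 200 | 157 | 0 | 23 |
| 222 | 179 | 0 | 1 |
| 223 | 180 | 0 | 0 |

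The arithmetic is sound. The band that depends on how the entry is read is 223 − 183 = 40 ms wide. The first two lines of reasoning hold only if Table 2 is a hard limit.

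**Is it a hard limit?** The asterisk sits on the item that tells sites to check Table 2, so the note is part of that instruction. Its last sentence adds a condition expressed relative to each patient's own conduction, which a single table entry cannot express. Telling a site to programme a delay short enough presupposes that the site has some choice. The note's mention of Table 2 occurs in the sentence on the seated wait and says nothing about precedence.

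**What reaches the analysis?** The study has no hypotheses (Protocol 7.3) and all analyses are exploratory (12.4). SAP section 8 restricts the data of interest by DDD-CLS pacing mode and does not mention AV delay. The SAP's tilt-test tables contain no AV-delay variable. Device programming is recorded at baseline (Protocol 9.2.1), and the PR interval is summarised (SAP 7.2).

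**Size if such patients were dropped.** The share affected is unknown, so this is illustration only. With 20 enrolled, fewer than 15 remain if 6 or more drop out. Taking the number as binomial(20, p), that probability is 1% for p = 10%, 20% for p = 20%, 58% for p = 30% and 87% for p = 40%. At p = 0 it is nil.

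**The case for a change.** The strongest case for a change is textual. The asterisk follows the clause on unlisted parameters, and the AV-delay row carries no mark, so the qualifying reading has to be inferred. Even on that reading, nobody says whether 180 to 140 ms is a range or one setting, or whether a value below 140 ms complies. The dropout rule applies for any reason and so could be stretched to this case. The study runs in at least two sites (Protocol 8.1.7), and deviation forms can be triggered automatically (15.2). One or two sentences would end the doubt.

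It stands that no sentence ranks the note against the table and that the dropout and no-waiver rules do not name this case. The documents do not settle it, and I do not settle it here.

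What does not follow is harm. Investigators are trained on the procedures (Protocol 4.6, 6.5), and sponsor staff may support programming (9.4), so a site in doubt has someone to ask. The thresholds rest on terms the documents leave undefined, and device detail is referred to the user manual (4.1). Eligibility is only partly visible, because replacements must also meet the BIOSync criteria, which the protocol cites but does not list. The remedy may not be cheap either: under Protocol section 14 a change with impact on study procedures is substantial and needs ethics approval before use.

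**Conclusion.** No change to the plan follows. The two instructions conflict only if Table 2 is a hard limit: below 183 ms, or below 223 ms if the entry is one setting with a nominal value of 180 ms. Both figures assume a common basis of measurement. The likelier reading is that the note qualifies the AV-delay row, which removes the conflict. Confidence in a true contradiction is therefore moderate at most.

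The number of patients concerned cannot be derived and may be zero, and no estimate in this descriptive study is shown to be biased. The probabilities of falling below 15 patients apply only if sites treated such patients as dropouts, and then only at assumed shares. What remains is a gap in detail that sites and sponsor would probably fill sensibly through training and programming support, with the settings on record. If a site raises the case, reconciling the two passages is for the sponsor. Nothing here says which delay or which rule is right.

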**Table 2 – Device programming**

Parameter	
Pacing Mode	DDD-CLS
Basic rate	50 bpm
Maximum CLS rate	120 bpm
Upper tracking rate	130 bpm
Atrioventricular delay	Low; 180–140 ms
Atrioventricular hysteresis mode	IRSplus
CLS Resting Rate Control	OFF
Atrial pacing polarity	Unipolar
Ventricular pacing polarity	Unipolar

9.2.3 Head-up tilt test

The HUTT will be performed according to the Italian protocol (9) and patient's hemodynamics will be continuously monitored during the entire test. Specifically, an external monitor will be used for continuous measurement and recording of systolic and diastolic BP, HR, SV, and TPR.

Prior to the start of the HUTT, a trained member of the study team will prepare the patient and set up the equipment needed for the test as follows:

- patient shall be supine on the tilt table and secured to it with the BP sensor cuff of the external monitor on his/her finger. Hand wearing the pressure sensor shall be placed on the chest at about 10 cm from heart and held in this position throughout the test;
- ECG leads shall be placed on patient’s chest and a BP cuff on his/her arm;
- If used, a high-definition camera may be placed to contemporarily pick up both patient and the external monitor positioned close to the tilt table.

**Note: video recordings of the entire test shall not be provided to the Sponsor and will be destroyed immediately after the examination. The investigator will assess the time of symptoms onset and will report it in the CRF.**

After 10 minutes in supine position, the patients will be tilted to 70° using an electronically operating tilt-table with a footboard.

### 9.2.3.1 Timing of tilt down

In this study the HUTT will not be performed for diagnostic purposes but rather to verify the proper functioning of the implanted pacemaker. Therefore, HUTT is aimed to induce the vasovagal reflex, confirmed by the onset of symptoms and by onset of pacing and not to induce syncope. Given ethical issues, the table will be tilted down at the time of loss of consciousness. In case of negative test, the table will be tilted down at the end of test-time.

The following procedures shall be conducted after HUTT completion:

- Document outcome measurements on the CRF;
- Provide continuous electrocardiogram traces printed at 5 mm/sec from the time of maximum spontaneous HR increase during phase 1 until the end of the exam.

## **9.3 Termination and post treatment**

The patients terminate the study regularly after the completion of the enrollment visit including HUTT and collection of study data. The CRF 'Study termination' has to be filled in. In case of any premature study termination, the CRF Study Termination has to be completed with the reason for study termination. The process of consent withdrawal is described in section 8.2.3.1.

After study termination the patients will continue to be treated according to standard routine care. The device programming is at the investigator's discretion.

## **9.4 Description of those activities performed by sponsor representative**

Sponsor representatives may support the investigator for pacemaker programming and interrogation or for the download of data of the programmer as needed.

Monitoring will be performed by Sponsor representatives according to the monitoring plan.

## **9.5 Possible influencing factors on outcome or interpretation of results**

No factors that could influence the outcome or interpretation of the results are known at time of protocol drafting.

## 10 RESPONSIBILITIES

### 10.1 Responsibilities of the sponsor

The sponsor of the BIO|Sync-HUTT study is:

BIOTRONIK SE & Co. KG  
[name]  
[name]  
Germany

The sponsor ensures that all documents, information and necessary human resources are made available for initiation, conduct and termination of the study.

In addition, the sponsor is obliged to fulfill the following tasks (selection of items):

- Maintaining insurance cover or indemnification of patients in case of injury in accordance with applicable laws.
- Contracting of investigational sites and investigators.
- Responsibility for all payments and financial coverage of the study.
- Selection of suitable investigational sites, investigators and clinical monitors.
- Creating a Master template for informed consent form and obtain approval of the Master template by the leading ethical committee (EC), if required.
- Obtaining of a favorable ethics vote(s) for conduct of the clinical study.
- Obtaining approval of the involved competent authorities (if applicable).
- Supervision of study conduct according to the legal regulatory requirements and the requirements of the CIP.
- Fulfill reporting duties of the sponsor to the ethic committees and regulatory authorities.
- Data analysis and data management.
- Performance of on-site audits as planned routine audits, on demand in case of detected non-compliances, or as preparation for an announced inspection by a Competent Authority.
- Provision of the final clinical investigation report (CIR) in accordance with applicable legal requirements and ethical principles.

#### 10.1.1 Project management

The clinical project manager is responsible for the following (selected items):

- Development of the clinical investigation plan and possible amendments.
- Coordination of all study-related activities dedicated to the sponsor.
- Support of investigational sites during the study (obtaining ethic committee votes, etc.).
- Continuous information of investigational sites and clinical monitors on study progress.
- The clinical project manager is supported by other staff members of the sponsor (e.g. in-house clinical research associates, data assistants, data base managers).

#### 10.1.2 Data management

The data manager is responsible for the following items (selection of items):

- Development and maintenance of the clinical data management system (CDMS; iMedNet of the company MedNet Solutions Inc, Minnetonka, MN 55305 USA).
- Development of the data management plan.

- Development of the CRF user guide.
- Data management.

### 10.1.3 Biostatistician

The statistician is responsible for the following items (selection of items):

- All statistical aspects within the clinical investigation plan.
- Statistical analysis for clinical investigation report.

The statistician will be supported by other staff members of the sponsor.

### 10.1.4 Monitor

The sponsor names clinical monitors for each participating investigational site prior to initiation of the respective site. Names and contact data will be provided to the investigational sites in due time. In case of changes, the investigational site will be informed by the sponsor. An adequate monitoring will be ensured by the sponsor. Monitoring will be conducted according to the SOPs of the sponsor. Responsibilities of the clinical monitors are described in section 11 of this document.

## **10.2 Responsibilities of the investigators**

### 10.2.1 Coordinating investigator

This study is coordinated by:

IRCCS Istituto Auxologico Italiano

Faint & Fall programme, Dept. of Cardiovascular, Neural and Metabolic Sciences, Ospedale San Luca

[name]

[name]

The responsibilities of the CI are listed in the following:

- Development and review of the clinical investigation plan.
- Procurement of the central vote of an ethics committee.
- Performance and progress control of the study.
- Continuous assessment of the risk/benefit ratio.
- If necessary, decision on premature study termination in consultation with the sponsor.
- Contribution to coordination of publication and presentations of study results.
- Advising all investigators in medical questions related to the study or study conduction.
- Evaluation of potential unexpected adverse events.
- Discussion of possible interim results.
- Cooperation in writing of the final clinical report.

The coordinating investigator is supported by the clinical Project Manager and other members of the sponsor.

In addition, the CI has the same rights and duties as other principal investigators.

